8 STUDY ASSESSMENTS AND PROCEDURES

8.1 ENDPOINT AND OTHER NON-SAFETY ASSESSMENTS

Screening and Eligibility Assessment – To be enrolled/consented in the Effectiveness trial, a patient must have screened positive for OUD and a MHS in the past six months AND currently meet clinical criteria for ≥2 symptoms of OUD on the DSM-5 checklist *AND/OR OUD diagnosis recorded in the electronic medical record AND a patient encounter in the last 6 months OR OUD diagnosis on problem list PCP reviewed in the last 6 months.*

Survey Administration – Surveys will be administered at baseline, and at 3- and 6-month follow-ups.

Construct/Instrument	Baseline	3-Month Follow-Up	6-Month Follow-Up
Demographics	X		
Social Determinants	X		
Homelessness Screening Clinical Reminder	X		
Legal involvement question (Addiction Severity Index – modified)	X		
Insurance	X		
Pain (PEG)	X	X	X
Alcohol Use (AUDIT)	X	X	X
Opiate Use (BAM-R)	X	X	X
Opiate Craving Question (Addiction Severity Index – modified)	X	X	X
Readiness to Change (ICR)	X		
Other Drug Use (BAM- R)	X	X	X
Recent Experience of Overdose	X	X	X
Health Related Quality of Life (Veterans Short Form-12)	X	X	X
Depression (SCL20)	X	X	X
Anxiety (Neuro-QOL Measure - Anxiety, Short Form)	X	X	X
Trauma (PC-PTSD-5 Criteria A screener)	X	X	X
PTSD (PCL-5)	X	X	X
Access to Care (SPIRIT Perceived Access Inventory)	X	X	X
Service Utilization	X	X	X
Medication Use	X	X	X
Side Effects	X	X	X

Care Management Tracking System (CMTS) – After the last study participant has completed the 6-month follow-up, we will extract information from CMTS. CMTS is a web-based registry hosted by the AIMS Center and used by the care managers to track process and outcomes.²⁰ The CMTS contains clinic-level process of care and patient-level clinical outcome data that shows how patients receive care. For the evaluation, CMTS will be used to measure the number of care manager encounters, the number of

care manager encounters with recorded elements of BA, number of psychiatric case reviews, urine test results, medications prescribed for OUD and MHS, as well as results of state prescription drug monitoring checks to obtain an objective measure of MOUD initiation and adherence. For injectable buprenorphine or naltrexone, clinic staff will likewise record the administration of these injections in the CMTS.

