Here the outcome measured at time t , for subject i , in clinic c is denoted by Y_{cit} . To account for the cluster-randomization this model includes a random effect for each clinic denoted as u_c . In order to allow a general longitudinal correlation and variance structure we use three subject-specific error terms denoted by u_{cit} for $t=0, 3, 6$ months. We assume a general 3×3 covariance model for these error terms to provide maximal validity to inference regarding change over time. To allow for potential non-linear change over time, we will enter time as a nominal variable by including dummy codes for the 3 and 6 month time points represented by the variables (3 months) and (6 months). Intervention main effects and interaction between intervention and time indicators capture the difference between intervention clinics and control clinics at each wave – with β_1 representing the adjusted mean difference across intervention groups at baseline (adjusting for the design variables) -- with $\beta_1 + \beta_4$ representing the adjusted mean difference across intervention groups at 3 months – and with $\beta_1 + \beta_5$ representing the adjusted mean difference across intervention groups at 6 months. Therefore, the primary contrasts are given by with β_4 as the 3-month intervention effect, and β_5 as the 6-month intervention effect. Note that each intervention effect accounts for the potential imbalance of outcomes across the intervention and control groups at baseline due to the small number of clusters (β_1) and this is removed from the cross-sectional mean contrasts at each follow-up time to define the key intervention effect parameters. *DesignVars* denotes a vector of covariates that includes: 1) low vs high fidelity, which must be controlled because it was a design/stratification variable for some clinics, and 2) additional covariates theoretically related to both the primary outcome and the probability of not completing follow-up surveys which will aid in enhancing validity against missing data and improving precision of estimation. Specifically, we will include: 1) worried about not have stable housing in the next two months, 2) being on parole or probation and/or presently awaiting charges, trial or sentencing, 3) opioid craving, 4) pain, 5) Audit-C, 6) provider trust (APAC item #6), and 7) any use of other drugs (dummy coding for each class of drug). The pre-specified primary effect of interest will be β_5 , which represents the difference in change from baseline between intervention and control clinics at 6 months. Table S2 presents a shell table for the primary outcome and Figure 2 presents a shell plot. Table S3 presents a shell table for the secondary outcomes.

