
For the primary outcome (mental health related quality of life [0-100]) we will use a linear mixed model with a normal distribution with a linear link function and model structure given above in Equation 1. For the primary outcome days-using-opioids [0-30] we will modify the above linear mixed model and adopt a similar regression structure using a generalized linear mixed model with binomial distribution logit link function. We will retain the random effect structure to include a random effect for clinic and include the time-specific subject-level error terms to both allow for binomial overdispersion and a general longitudinal covariance over time. For the secondary and exploratory outcomes, appropriate link functions will be used for linear, binary (logit), ordinal (logit), and count (Poisson/negative binomial depending on dispersion) data. For any binary longitudinal outcomes, we will simplify the subject-level random effects to be a simple random intercept due to identifiability (no overdispersion and only correlation).

Effect sizes. Cohen's d effect sizes will be calculated and presented with 95% confidence intervals. Between group effect sizes will be calculated as the model-estimated treatment effect at each time point divided by the pooled, raw baseline standard deviation.

Testing of Multiple Primary Outcomes. The intervention will be interpreted to have been successful if there is a significance group difference between either primary outcome, not necessarily both primary outcomes. Corrections for multiple testing will be computed using a Bonferroni correction for the two multiple primary outcomes and therefore we will use an $\alpha=0.05/2 = 0.025$ to test each primary outcome. All secondary outcomes are exploratory and no multiple testing adjustment will be used. We will present secondary and exploratory outcomes descriptively using a forest plot to illustrate the collection of associations with intervention.

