The DSMB directed the research team to discontinue consenting new patients into the trial for reasons of futility due to the current rate of recruitment. Therefore, we present a revised power analysis calculated before the outcome data are to be unmasked. The revised power analysis is based on the observed number of patients enrolled (n=254), observed number of clinics enrolling ≥ 1 patient (n=28), the observed coefficient of variation (0.97) which represents the variation in cluster sizes, and the Intraclass Correlation Coefficients (ICCs) estimated for interim analysis requested by the DSMB. For the masked interim ICC estimation we used all patient data available on 11/7/2022, including N=191 in the baseline sample and N=155 in the 6-month follow-up sample. We adjusted for treatment group and baseline primary outcomes. We used the jackknife method to compute a standard error by computing ICCs deleting each cluster in turn and then averaging these estimates.¹⁶ For the 6-month follow-up, the opioid use ICC was estimated to be 0.00 (SE= 0.02). For the 6-month follow-up, and the MCS ICC was estimated to be 0.03 (SE=0.09). Based on these estimates, and using a Bonferroni correction to account for multiple outcomes, we will have 80% power to detect a medium effect size of 0.40 for days of opioid use and a medium effect size of 0.46 for MCS. This represents a difference of 2.65 (e.g., 15.00 days compared to 12.3 days) days using opioids and a difference of 6.22 (e.g., 40 compared to 33.8) on the MCS between the intervention and control groups.

7. References

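### The primary contrast is a difference in change from baseline, which is less precise than adjusting for the baseline outcome and may not deliver the detectable effects stated in SAP 6

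*SAP*

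**What the plan says.** SAP 4.1, Equation 1, treats the baseline, 3-month and 6-month values as responses. It has a free arm difference at baseline (β1), arm-by-time interactions, one clinic effect that is constant over time, and an unstructured 3×3 patient covariance. The primary effect is β5, "which represents the difference in change from baseline between intervention and control clinics at 6 months". The SAP's reason is that each effect "accounts for the potential imbalance of outcomes across the intervention and control groups at baseline due to the small number of clusters", and that "this is removed from the cross-sectional mean contrasts at each follow-up time to define the key intervention effect parameters".

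The covariates are fidelity, housing worry, legal status and "3) opioid craving, 4) pain, 5) Audit-C, 6) provider trust (APAC item #6), and 7) any use of other drugs". The vector carries no time index. The baseline value of the outcome is not in it, although the outcome is collected then (Protocol 8.1: "Surveys will be administered at baseline, and at 3- and 6-month follow-ups").

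SAP 6 states 80% power for standardized effects of 0.40 (opioid days) and 0.46 (MCS). Its inputs are 254 patients, 28 clinics, a cluster-size coefficient of variation of 0.97, and ICCs of 0.00 and 0.03. Of the model behind those ICCs it says: "We adjusted for treatment group and baseline primary outcomes". It gives no baseline to 6-month correlation and no attrition.

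**The concern.** A change score carries the measurement noise and short-term variation of two occasions. Conditioning on the baseline value also deals with chance imbalance, but it subtracts only the part of baseline that predicts the outcome. The SAP expects its covariates to improve precision, yet a term that is constant over time drops out of a difference in change.

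Enrolment stopped at 254, so precision is scarce. The ICCs were estimated with baseline adjustment while the test is made without it. The stated detectable effects may therefore describe a contrast other than the one to be tested.

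**Working it through.** **Inputs.** N = 254, 28 clinics (mean 254/28 = 9.07), CV 0.97, ICC 0.00 (SE 0.02) for opioid use and 0.03 (SE 0.09) for MCS, all from SAP 6. Alpha is 0.025 per outcome (SAP 4.1: "Corrections for multiple testing will be computed using a Bonferroni correction for the two multiple primary outcomes"), two-sided (Protocol 9.4.2). Equal arms are assumed. The correlation r is in neither document; 0.3 to 0.7 is assumed.

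**1. The stated effects.** With SD 1, the detectable effect is (z₀.₉₈₇₅ + z₀.₈₀) × √(4·DEFF/N).
- Opioid use, DEFF = 1: (2.241 + 0.842) × √(4/254) = 0.387. With a t distribution on 26 df it is 0.407. Stated: 0.40.
- MCS: generalized least squares (GLS) weights over clinic-size patterns with CV near 0.97 give 0.463 (range 0.459–0.467), so DEFF ≈ (0.463/0.387)² = 1.43. Stated: 0.46.

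Both figures reproduce approximately as a comparison of 6-month values with all 254 analysed. No single variant matched both exactly.

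**2. Variance per patient (equal SDs over time, no clinic effect).**
- 6-month value alone: 1
- Change: 1 + 1 − 2r = 2(1 − r)
- Baseline-adjusted: 1 − r²

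The SE ratio of change to adjusted is √[2(1 − r)/(1 − r²)] = √[2/(1 + r)], which exceeds 1 for every r below 1. Its square is the equivalent increase in patients: 54%, 33% and 18% at r = 0.3, 0.5 and 0.7.

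**3. Opioid use (ICC 0, normal approximation).**

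| r | SE excess of change | Detectable: change | Detectable: adjusted | Power at 0.40: change | Power at 0.40: adjusted |
|---|---|---|---|---|---|
| 0.3 | 24% | 0.458 | 0.369 | 67.5% | 86.4% |
| 0.4 | 20% | 0.424 | 0.355 | 74.8% | 89.2% |
| 0.5 | 15% | 0.387 | 0.335 | 82.8% | 92.5% |
| 0.6 | 12% | 0.346 | 0.310 | 90.7% | 95.9% |
| 0.7 | 8% | 0.300 | 0.276 | 97.0% | 98.7% |

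The r at which the change contrast just meets 0.40 is 1 − ½(0.40/0.387)² ≈ 0.47, or 1 − ½(0.40/0.407)² ≈ 0.52 with 26 df.

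**4. MCS (ICC 0.03, constant clinic effect).** The clinic effect cancels from β5, so its variance stays at 2(1 − r) with no design effect.

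| r | Detectable: change | Detectable: adjusted (GLS) | Power at 0.46: change |
|---|---|---|---|
| 0.3 | 0.458 | 0.410 | 80.4% |
| 0.5 | 0.387 | 0.359 | 92.3% |
| 0.7 | 0.300 | 0.288 | 99.4% |

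The ratios 0.458/0.410, 0.387/0.359 and 0.300/0.288 give excesses of 12%, 8% and 4%. Depending on how clinic-level baseline information is used, GLS gives up to about 16%, 11% and 6%. The change contrast meets 0.46 from r = 1 − ½(0.46/0.387)² ≈ 0.29.

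**5. Attrition.** The 20% in Protocol 9.2 leaves about 203 patients, so 0.387 becomes 3.083 × √(4/203) = 0.433. The required r rises to 1 − ½(0.40/0.433)² ≈ 0.57 for opioid use and, by the same formula, to about 0.43 for MCS.

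**6. Covariates.** With complete data in the linear model, β5 is the arm difference in (6-month mean − baseline mean). A covariate term that is the same at both times subtracts out. Fitting Equation 1 by exact GLS with such covariates left the SE of β5 unchanged.

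**The case against.** The SAP chose this contrast deliberately and gave a reason. The estimate is not biased by the choice, and the model is general ("In order to allow a general longitudinal correlation and variance structure we use three subject-specific error terms"). All of that stands. None of it restores the precision, and conditioning on baseline also handles the chance imbalance that the SAP cites.

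A reader might infer that the trial is underpowered. The documents do not support that, because r is not given. At r of about 0.5 or more with all 254 analysed, the change contrast meets both stated effects to within about 2 power points.

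A reader might also carry the ICC 0 algebra over to MCS and expect power at 0.46 well below 80% at r = 0.3. Under Equation 1 the clinic effect cancels and power there is about 79–80%. Likewise, the rule that change is worse than ignoring baseline when r is below 0.5 holds only without a clinic effect. For MCS the break-even is 1 − 1.43/2 ≈ 0.28. If clinic effects drift over time, which Equation 1 does not model, the MCS position weakens: the detectable effect at r = 0.3 is 0.489 with clinic autocorrelation 0.8.

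Four limits also stand.
- Opioid days use a binomial-logit mixed model, so the algebra is approximate there, and adding a baseline covariate changes which conditional odds ratio is estimated.
- With missing follow-up, the likelihood uses the baseline data, so equality with the simple change difference is exact only for complete data. The covariates may still help with missingness.
- Clinics are randomized before patients consent (Protocol 1.3), and one exclusion applies to intervention clinics only (Protocol 5.2, item 4). Baseline differences could therefore be systematic, in which case change and adjusted analyses answer different questions.
- The SAP's change log runs to August 2024 and mentions model convergence, so fitting may have begun. Changing the primary contrast after unmasking would be post hoc.

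**Conclusion.** The concern holds as a loss of precision. In the linear complete-data model, β5 has an SE about 24%, 15% or 8% larger than the baseline-adjusted contrast at ICC 0 and r = 0.3, 0.5 or 0.7. For MCS at ICC 0.03 with a constant clinic effect, the excess is roughly 12–16%, 8–11% or 4–6%. The listed covariates do not reduce it.

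Whether the stated detectable effects are met depends on the missing r. Opioid use needs about 0.5 or more, and MCS about 0.3, with no attrition. That is a real risk for opioid use and a smaller one for MCS; a shortfall is not demonstrated for either. The MCS figures take 0.03 as the unadjusted ICC because the documents give no other, although it came from a baseline-adjusted model and has an SE of 0.09.

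**What to change.** **If outcomes are still masked.** In SAP 4.1, use only the 3- and 6-month values as responses. Add the patient's baseline value of the outcome and its clinic mean as covariates, and take the adjusted 6-month arm difference as primary. Use the same structure on the logit scale for opioid days, and note that the conditional odds ratio differs from the present one. Keep β5 as a sensitivity analysis; it is also informative if baseline imbalance is systematic.

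**If outcomes are already unmasked.** Keep β5 primary and report the adjusted contrast as a labelled sensitivity analysis.

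**In either case.** Do not force a common baseline mean in the two arms. Consent follows clinic randomization and one exclusion applies to one arm only, so that constraint could bias the estimate. Restate the detectable effects in SAP 6 for the chosen contrast, using the observed r from masked data and the expected attrition. Label the 6-month rows of Table S2 with the contrast reported, since as they stand they do not say whether it is β5 or β1 + β5.

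**Cost.** SAP wording, one masked estimate of r per outcome and a revised power paragraph. No new data or patients are needed. The choice of primary contrast must be settled, and dated, before unmasking.

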variable of interest will be group randomization status (e.g., intervention versus control). Main effects and interaction terms with time-indicator variables capture the difference between intervention and control group at each wave. Covariates will be included if they are theoretically related to both the dependent variable and the probability of having missing data. An alpha level of 0.05 and two-tailed tests will be used to determine statistical significance. Results will be presented as adjusted differences between groups with confidence intervals. **Missing Data** - We will examine patterns of missing data to determine the degree to which the missing at random assumption (the degree to which missingness is related to variables included in the model) is plausible. With high missing rates, we may use missing data methods to account for missing not at random mechanisms. If warranted, multiple imputation or similar methods will be used to account for missing data on completed or partially completed baseline and follow-up surveys (e.g., skipped items).

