COLLABORATING TO HEAL ADDICTION AND MENTAL HEALTH IN PRIMARY CARE (CHAMP)

STATISTICAL ANALYSIS PLAN (SAP) **1/24/2023**

Multiple Principal Investigators - [name]; [name]; [name]

Authors - [name], [name], [name]

Version - 5.0 (8/30/2024)

Grant Number: UF1MH121942

National Clinical Trial (NCT) Identified Number: NCT04600414

Sponsor: National Institute of Mental Health (NIMH)

Modifications to the CHAMP Statistical Analysis Plan

Change	Reason	Date
In shell Table S2 changed " Change to 3 months " to " 3 months " and " Change to 6 months (primary outcome) " to " 6 months (primary outcome) "	To simplify the calculation of the SE for the adjusted mean differences in order to calculate the confidence interval	5/6/24
Replacing adjusted mean difference with AOR for opioid use primary outcome	Calculating SE for adjusted means from logistic model requires use of the delta method, so	6/18/24

Reporting Cohen's d without confidence intervals	confidence intervals are less interpretable (i.e., contain 0 for significant effects)	
	We will report confidence intervals for the AOR. (see above regarding calculating SE for logistic model).	6/18/24
Test moderated mediation by analyzing moderation first	Because we planned to conduct these analyses separately (mediation, then moderation), the presence of a moderation of $M \rightarrow Y$ violates an assumption of mediation.	8/8/24
Added mean, standard deviation, and 95% confidence intervals to secondary outcomes table (Table S3). Omitted recent overdose covariate from main models.	To provide additional detail to assist with interpretation of secondary outcome results. To help with model convergence.	8/30/24

Table of Contents

1. Introduction	4
2. Study design	4
3. Outcomes	4
4. Analyses	6
4.1. Primary and Secondary Outcomes (Hypotheses 1 and 2).....	6
4.2 Moderated Mediation Analyses (Hypothesis 2)	8
5. Missing data	9
6. Power Calculation	10
7. References.....	11
8. Shell Tables and Figures	13
Table S1. Baseline characteristics of patients enrolled in SPIRIT	13
Table S2. Multiple primary outcomes across intervention conditions.....	17
Table S3. Treatment effects for secondary and exploratory outcomes at 3 and 6 month follow-up....	18
Table S4a. Moderation analysis.....	20
Table S4b. Mediation analysis	20

1. Introduction

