	Overall n (%) or μ (SD)	Intervention Group n (%) or μ (SD)	Control Group n (%) or μ (SD)
Age (years)			
Are you of Hispanic, Latino/a/e or Spanish origin?			
Yes			
No			
Missing			
Race			
American Indian, Alaska Native, or other Indigenous group			
Native Hawaiian or other Pacific Islander			
African American or Black			
White			
Multi-race			
Another Identity			
Missing			
Current Gender Identity			
Man			
Woman			
Non-binary or gender fluid			
Missing			
Marital Status			
Divorced			
Married or living with a partner			
Separated			
Single, never married			

Missing

Housing Status

No, not living in stable housing

Yes, living in stable housing

Missing

Concern about Future Housing

No, not worried about housing in the near future

Yes, worried about housing in the near future

Missing

Parole/Probation

No

Yes

Missing

Awaiting charges, trial, or sentencing

No

Yes

Missing

Currently mandated by a court to receive addiction treatment

No

Yes

Missing

Individual Readiness to Change (ICR; range: 0-10)

Importance for change

Confidence for change

Readiness for change

Clinical Characteristics:

Veterans Short Form 12 Mental Health Component Summary score

(MCS; range: 0-100)

Opioid Use:

Any opioid use in the past 30 days

Number of days of opioid use in the past 30 days

Opioid Craving:

Not at all

Slightly

Moderately

Considerably

Extremely

Medication for OUD:

Lifetime

Current

Alcohol Use: (AUDIT-C; range: 0-12)

Other Drug Use: Any use in the past 30 days

Cocaine and/or crack use

Other stimulant use

Sedative and/or tranquilizer use

Cannabis use

Inhalant use

Other illegal drug use

Recent Overdose Experience

Ever overdosed

Number of previous overdoses

Overdosed in the past 6 months

Number of overdoses in the past 6 months

Pain Level (PEG; range: 0-10)

Hopkins Symptoms Checklist (SCL-20; range: 0-4)

Anxiety (PROMIS Measure - Anxiety 8a - Adult v1.0: range: 36.4-76.8)

PTSD Checklist (PCL-5; range: 0-80)

Table S2. Multiple primary outcomes across intervention conditions

	Intervention		Control		Treatment Effects		
	Mean (SD)	95% CI	Mean (SD)	95% CI	Adjusted Odds Ratio	95% CI	Cohen's d
Opioid Use							
Baseline							
3 months							
6 months (primary outcome)							
					Adjusted Mean Difference	95% CI	Cohen's d
MCS							
Baseline							
3 months							
6 months (primary outcome)							

Table S3. Treatment effects for secondary and exploratory outcomes at 3 and 6 month follow-up

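### For opioid days, the only between-arm effect with an interval is a conditional odds ratio; no adjusted difference in days with an interval is planned

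*SAP*

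**What the plan says.** - **Model.** SAP section 4.1 analyses days of opioid use with a "generalized linear mixed model with binomial distribution logit link function". On the random effects it says: "We will retain the random effect structure to include a random effect for clinic and include the time-specific subject-level error terms". The pre-specified effect is beta5, the between-arm difference in change from baseline to 6 months.
- **Effect measure.** The SAP's modifications table, dated 6/18/24, records: "Replacing adjusted mean difference with AOR for opioid use primary outcome". The logged reason is that standard errors for adjusted means need the delta method, and that "confidence intervals are less interpretable (i.e., contain 0 for significant effects".
- **Table S2.** The opioid block gives each arm's mean, SD and 95% interval at baseline, 3 and 6 months. The treatment-effect columns are "Adjusted Odds Ratio", its 95% interval, and Cohen's d without an interval. The MCS block keeps an adjusted mean difference.
- **Cohen's d.** SAP section 4.1 defines it as the model's treatment effect divided by the raw pooled baseline SD.
- **Protocol 9.4.2**, on the primary outcomes: "Results will be presented as adjusted differences between groups with confidence intervals".
- **SAP section 6** gives 80% power for a standardised effect of 0.40 and adds: "This represents a difference of 2.65 (e.g., 15.00 days compared to 12.3 days) days using opioids".

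**The concern.** The outcome is a count of days and its power is worked out as a difference in mean days, but the planned effect estimate is on the log-odds scale. The odds ratio compares the odds of a use day between arms with the clinic and patient effects held fixed. The SAP does not label it conditional; that follows from the model. When patients differ widely, it lies further from 1 than the population-average odds ratio, and by itself it does not say how many days of use were averted.

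At stake is how one of the two primary results is read. The trial could report a clear odds ratio with no adjusted estimate, and no statement of precision, in the unit of its own question and of its own power statement. The reason logged for the change makes this more pressing: if the logit test and the day-scale interval can disagree, a reader needs to see it.

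**Working it through.** **1. Reproduce the power figure and confirm its scale.** Inputs from SAP sections 4.1 and 6: N = 254, opioid ICC = 0.00 (so the design effect is 1 whatever the cluster-size variation), d = 0.40, alpha = 0.05/2 = 0.025. The test is two-sided (Protocol 9.4.1). An equal patient split is assumed.

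- SE of d = sqrt(4/254) = 0.1255. Noncentrality = 0.40/0.1255 = 3.19.
- Noncentral t with 28 − 2 = 26 df gives power 78.5%, against the stated 80%. The normal approximation gives 82.8%.

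The figure is reproduced as a comparison of means. No odds ratio enters it. The implied SD is 2.65/0.40 = 6.625 days, which the documents do not state.

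**2. Convert an odds ratio to days.** Mean days = 30 × E[expit(μ + σZ)], with Z standard normal and σ the combined random-effect SD on the logit scale. Solve μ for the control mean, then shift μ by ln(OR). The documents give neither the outcome's control mean nor σ, so both are assumptions. The 15 days is the SAP's own example.

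By hand at σ = 0 from 15 days: OR 0.50 gives odds of 0.5, a probability of 1/3 and 10 days, a fall of 5.0. A fall of 2.65 gives 12.35/30 = 0.412, odds of 0.70, so OR 0.70. For σ above 0, numerical integration gives, from 15 days:

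| σ | Total SD (days) | Fall for OR 0.50 (days) | Conditional OR for a 2.65-day fall |
|---|---|---|---|
| 0 | 2.7 | 5.0 | 0.70 |
| 1 | 6.7 | 4.2 | 0.65 |
| 2 | 9.7 | 3.1 | 0.56 |
| 3 | 11.2 | 2.4 | 0.46 |
| 4 | 12.1 | 1.9 | 0.38 |

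At an assumed control mean of 5 days, OR 0.50 is a fall of 2.3 days (σ = 0) to 1.1 days (σ = 4). The same odds ratio can therefore lie on either side of 2.65 days.

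The row closest to the implied SD of 6.6 is σ = 1. There OR 0.50 is 4.2 days, and the population-average odds ratio is 0.56.

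**3. Check whether Cohen's d fills the gap.** Read literally for this model, d is a log-odds divided by an SD in days: ln(0.50)/6.625 = −0.693/6.625 = −0.10. The day-scale equivalent at σ = 1 would be 4.2/6.625 = 0.63 in size. The literal d is not on the scale of the 0.40 in SAP section 6.

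**4. Likely precision of a day-scale estimate.** With SD 6.625, N = 254 and ICC 0, SE = 6.625 × 0.1255 = 0.83 days. With 26 df the half-width is about 1.7 days for a 95% interval and 2.0 for a 97.5% interval. This is a simple comparison of means with no loss to follow-up, so it is only a guide.

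**The case against.** A reader might infer that the opioid result appears only as an odds ratio and cannot be read in days. Table S2 does not support that. It prints means, SDs and intervals in days for each arm at each visit, so a crude difference, and a crude difference in change, can be read off. Once the table is filled in, the control mean is known and much of the spread above narrows. Near the SD implied by the power statement, the gap between conditional and population-average odds ratios is modest (0.50 against 0.56).

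A reader might also treat 2.65 days as the benchmark for success. SAP section 6 presents it only as the difference detectable with the patients enrolled, and nothing calls it clinically meaningful.

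Nor is the change hidden. It is logged with a date and a reason, and Protocol 9.4.1 provides for a separate SAP. An odds ratio beside arm means is a conventional display for a logit model. A clinic-level bootstrap would mean refitting a mixed model with a 3 × 3 patient covariance over 28 clinics of very unequal size, in a plan that has already dropped a covariate to help convergence.

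All of that stands. It does not supply the missing quantity. Single-arm means with single-arm intervals give neither the covariate-adjusted difference in change, which is what beta5 targets, nor its interval. Cohen's d does not recover it either.

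**Conclusion.** The point holds as a gap in reporting. For a primary outcome measured and powered in days, the SAP plans no adjusted between-arm difference in days with an interval, and Protocol 9.4.2 is not met for that outcome. The documents do not support reading this as a fault in the test: the logit model, the beta5 contrast and the Bonferroni level are unaffected, and no sample-size figure changes.

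The size of the ambiguity rests on assumptions. From the SAP's 15-day example, an odds ratio of 0.50 spans about 5.0 to 1.9 fewer days over an assumed logit random-effect SD of 0 to 4. The illustration uses one normal random effect and no covariates.

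**What to change.** Keep the logit model, the beta5 test and alpha 0.025. Then:

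1. Add to the opioid block of Table S2 the model-standardised between-arm difference in change in mean days at 6 months, averaged over covariates and random effects. Take a percentile interval from parameter simulation. Use a clinic-level bootstrap only if the refits converge.
2. Label the odds ratio as conditional on clinic and patient effects.
3. Base the opioid Cohen's d on the day-scale difference.
4. Report the day difference beside the 2.65 days of SAP section 6, described as a detectable difference.

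The cost with simulation is a short post-estimation step and one column; the bootstrap would cost considerably more. Simulation removes the delta-method calculation but not the possible disagreement between scales. The day-scale interval may include 0 when the logit test is significant, and the SAP should say in advance that this will be reported and explained, with beta5 remaining the test.

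### The SAP's one Cohen's d rule does not fit the logit model for opioid days: applied to the effects the SAP defines, it divides a log odds ratio by an SD in days

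*SAP*

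**What the plan says.** The effect-size paragraph of SAP 4.1 has a single rule, not limited to any outcome. Cohen's d is the "model-estimated treatment effect at each time point divided by the pooled, raw baseline standard deviation", and section 4.1 adds that "effect sizes will be calculated and presented with 95% confidence intervals".

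The paragraph just before it sets the opioid model: "For the primary outcome days-using-opioids [0-30] we will modify the above linear mixed model", "using a generalized linear mixed model with binomial distribution logit link function". The regression structure carries over from Equation 1. There β4 and β5 are named as the 3-month and 6-month intervention effects, and β5 is the pre-specified primary effect, which "represents the difference in change from baseline between intervention and control clinics at 6 months".

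Table S2 gives opioid use an "Adjusted Odds Ratio" column with a 95% CI, then a Cohen's d column with no CI. The MCS block also shows d without a CI. In Table S3 the outcomes summarised by means have d with a CI, while alcohol, cannabis and other drugs have an odds ratio and no d.

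The modifications table (6/18/24) records "Replacing adjusted mean difference with AOR for opioid use primary outcome" and gives as reason "Calculating SE for adjusted means from logistic model requires use of the delta method, so" the intervals are harder to interpret. On the same date it records that d will be shown without an interval.

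SAP section 6 equates an effect size of 0.40 for opioid use with a difference of 2.65 days.

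**The concern.** The rule works when the model effect and the SD share a unit, as they do for the MCS and the other outcomes with a linear model. Under a logit link, β4 and β5 are log odds ratios. An analyst who applies the rule to the effects that section 4.1 names would divide log-odds by days. The result has units of 1/days, changes with the mean level of use, and cannot be compared with any other d.

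Opioid use in Table S2 is the only outcome in the shell tables where an odds ratio and a d stand side by side, so the gap falls on a primary outcome. A number on the wrong scale could make a real effect look negligible to a reader who knows the usual benchmarks, or who has just read that section 6 calls 0.40 a medium effect.

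**Working it through.** **Inputs.** From SAP section 6: 254 patients, 28 clinics, opioid ICC 0.00, Bonferroni correction, 80% power, d = 0.40, equivalent to 2.65 days (15.00 against a printed 12.3; I use 15.00 − 2.65 = 12.35). From SAP 4.1: 0–30 day scale, α = 0.025 per primary outcome. From protocol 9.4.1: two-tailed tests. Assumed: equal arms of 127 and no baseline difference between arms, so that the 6-month contrast equals the difference in change.

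**1. Reproduce the SAP's 0.40.** With ICC = 0 the design effect is 1, so the SE of d is √(4/254) = 0.1255. With a t reference on 28 − 2 = 26 df, the detectable d is 0.407 and power at 0.40 is 78.5%. The normal approximation gives 0.387 and 82.8%. The stated figure is reproduced to rounding. It is a days-scale d.

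**2. Implied SD.** 2.65 / 0.40 = 6.625 days. The SAP gives no baseline SD, so this value is solved back from the power statement.

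**3. d on the days scale.** −2.65 / 6.625 = −0.40. This holds by construction, given step 2.

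**4. The rule applied to the logit effect.**
- logit(15/30) = 0
- logit(12.35/30) = −0.357 (odds ratio 0.70)
- −0.357 / 6.625 = −0.054 per day, smaller than step 3 by a factor of 0.40/0.054 ≈ 7.4

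**5. Conditional coefficient.** Step 4 uses a marginal log odds ratio. The planned model has subject-level terms, so its coefficient is conditional and larger. The documents give no subject-level SD, so I assumed normal effects with a logit SD of 1 to 4 and solved for the coefficient that gives marginal means of 15 and 12.35 days.

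| Logit SD (assumed) | Log odds ratio | Divided by 6.625 |
|---|---|---|
| 1 | −0.432 | −0.065 |
| 2 | −0.588 | −0.089 |
| 3 | −0.776 | −0.117 |
| 4 | −0.977 | −0.147 |

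**6. Dependence on the mean.** Keep the 2.65-day difference and the 6.625 SD, but use 5 versus 2.35 days (assumed). The marginal log odds ratio is −2.465 − (−1.609) = −0.856, and the quotient is −0.129. The days-scale d is still −0.40.

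**7. Naming days is not enough.** Predicted days can be averaged over the random effects or taken at random effect zero. With the assumed logit SD of 1 to 4, the marginal d stays at −0.40. At random effect zero it runs from −0.48 to −1.03 for 15 versus 12.35 days, and from −0.34 to −0.06 for 5 versus 2.35 days.

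**The case against.** The strongest reply is that the SAP never says a log-odds is to be divided by the SD. Several places point to days. The delta-method reason in the modifications table makes sense only for back-transformed means, because a log odds ratio over an SD would not need it. Section 6 expresses the effect size in days. Table S3 gives no d to the outcomes reported as odds ratios, so the authors do not apply d mechanically to logit models. This stands. A reader might infer that the reported d for opioid use will be about seven times too small. The documents do not support that, because the factor follows only if the rule is applied to β5 itself, with a back-solved SD and a marginal log odds ratio.

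A second reply is that d decides nothing. Success rests on testing β5 at 0.025, and Table S2 prints group means with intervals and the odds ratio with its interval beside d. No passage commits the authors to comparing the observed d with 0.40 or with the MCS value. This also stands. A reader might infer that the primary analysis is compromised, and it is not.

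Neither reply supplies the missing rule. A modifications entry explains a change but does not define an estimator, and step 7 shows that an intention to use days still leaves the value open.

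**Conclusion.** The point holds as a defect of specification. For opioid use, SAP 4.1 leaves the scale of the numerator of d unstated, and the only effects it defines under the logit model make the rule invalid. In the SAP's own example the quotient would be about 0.05, or 0.065 to 0.147 with a conditional coefficient, against 0.40 on the days scale. These figures rest on the back-solved SD of 6.6 days, no baseline imbalance and, for the range, an assumed subject-level logit SD of 1 to 4. They show what the rule gives as written and do not predict what will be reported.

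Separately, section 4.1 promises 95% intervals for d, while Table S2 has none for either primary outcome. That is an inconsistency within the current text. The test of β5 and the rule for identity-link outcomes are unaffected.

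**What to change.** In SAP 4.1, limit the present d rule to outcomes fitted with an identity link. For opioid use choose one of two options:

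- Define d as the marginal (population-averaged) model-predicted difference in days, on the same baseline-adjusted contrast as β4 and β5, divided by the pooled baseline SD in days.
- Drop d for opioid use and report the adjusted odds ratio with its interval alone, as Table S3 does for the other substance-use outcomes.

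Then make the sentence on intervals for d agree with Table S2.

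The second option costs only wording and a deleted table cell. The first adds one post-estimation step to average predictions over the random effects. A bootstrap interval for d is optional. The authors gave a reason for reporting d without one, and refitting this model repeatedly over 28 clinics of very unequal size (coefficient of variation 0.97) would be real work when a covariate has already been dropped to help convergence.
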